8.3. Exploratory Immunogenicity Analyses

ELISA seroconversion and GMTs of the ELISA antibody against M-001 from Day 1 to Days 22, 43, 78, 172, and 200 will be presented in Table 44.

Table 26Table 27Table 28Table 29

These percentages will be summarized visually in box plots over time in Figure 6, Figure 7, Figure 8, and Figure 9, for selected cell subsets.

GMPs of influenza-specific CD4+ T cell subsets expressing discrete memory markers (CCR7, CD45RO, and CD57) will be summarized at baseline (Day 1) and on study days 15, 36, 43, 78, 172, 186, and 200 (Table 38), by study arm. The subject-level percentages corresponding to selected cell subsets will be presented in Figure 30. Analogous summaries will be presented for CD8+ T cells in Table 39and Figure 31.

The percentage of influenza-specific CD4+ cell subsets expressing IL-4 or IL-17, T follicular helper cells (CD4+, CXCR5+, PD-1+, IL-21+), T follicular regulatory (Tfr) cells (CXCR5+, PD-1+, CD25+, CD127+), and Tregs (CD25+, Foxp3+) measured by flow cytometry will be summarized at baseline (Day 1) and on study days 15, 36, 43, 78, 172, 186, and 200 (Table 40, Table 41, Table 42, and Table 43, respectively). Boxplots for these percentages will also be presented in Figure 32, Figure 33, Figure 34, and Figure 35.

9. SAFETY EVALUATION

All summaries and analysis of safety data will be presented for the Safety Analysis population. Safety summaries will be presented overall and by study arm.

Continuous variables will be summarized using the following descriptive statistics: n (non-missing sample size), mean, standard deviation, median, maximum, and minimum. All categorical measures will be summarized by the frequency and percentages of observed levels. The denominator for the percentages may be based on the number of non-missing observations for an assessment or based on the number of subjects in a population. This will be described for each table.

9.1. Demographic and Other Baseline Characteristics

Summaries of age, sex, ethnicity, race, BMI, and prior receipt of seasonal influenza vaccine will be presented by site (Table 17 and Table 18) and by vaccination group (Table 19 and Table 20). Age will be summarized as a continuous as well as categorical variable. Ethnicity is categorized as Hispanic or Latino, not Hispanic, and not Latino, Not Reported, or Unknown. In accordance with NIH reporting policy, subjects may self-designate as belonging to more than one race or may refuse to identify a race, the latter reflected in the eCRF as "No" to each racial option. BMI will be summarized as a continuous and a categorical variable, categorized as ($<30, \ge 30$). Self-reported history of prior receipt of seasonal influenza vaccine will be categorized by influenza season (2016-17 only, 2017-18 only, both 2016-17 & 2017-18, neither, or unknown).

Individual subject listings will be presented for all demographics (Listing 6).

9.1.1. Prior and Concurrent Medical Conditions

All current illnesses and past pre-existing medical conditions will be coded using the Medical Dictionary for regulatory affairs (MedDRA®) coded version 22.0 or higher.

Summaries of subjects' pre-existing medical conditions will be presented by MedDRA System organ class (SOC) and study arm (Table 21).

Individual subject listings will be presented for all medical conditions (Listing 7).

9.2. Measurements of Treatment Compliance

All subjects were to receive three study vaccinations administered in the clinic. The number of study vaccinations administered to subjects will be presented by vaccine group as part of the subject disposition table (Table 13).

9.3. Adverse Events

An overall summary of all adverse events will be presented in Table 45. A summary of adverse events occurring in 5% or more of subjects in any study arm will be presented in Table 46.

9.3.1. Solicited Events and Symptoms

Solicited injection site and systemic reactogenicity events will be documented from the time of each study vaccination (Day 1 (Visit 01) and approximately Day 22 (Visit 04)) through 7 days after each study vaccination. They were graded on a scale of 0 (none), 1 (mild), 2 (moderate), and 3 (severe). Systemic events include fever, feverishness, fatigue, malaise, myalgia, arthralgia, headache, and nausea, and the grading scale for these can be found in Table 7. The grading scale for fever is included in Table 8. Injection site events

include pain, tenderness, pruritus, ecchymosis, erythema, and induration/swelling. Ecchymosis, erythema, and induration are measured by both functional and measurement grading scales defined in Table 9 and Table 10, respectively.

When calculating the incidence of solicited events, each subject will be counted once at the highest severity following the applicable dose, and any repetitions will be ignored. For summaries presented separately for each vaccination, the denominator for percentages will be the number of subjects who received the respective vaccination with non-missing data for the event summarized. For summaries over all vaccinations the denominator will be the number of subjects who received at least one vaccination with non-missing data for the event summarized.

Additionally, solicited AEs will be analyzed by dichotomizing the response into a binary variable (none vs mild, moderate, or severe) and using 95% CIs calculated using Clopper-Pearson methodology from a binomial distribution (SAS Proc Freq with a binomial option) to summarize the proportion of subjects reporting each symptom, any injection site symptom, and any systemic symptom (Table 47). Summaries of solicited AEs will be presented separately for each study vaccination as well as overall study vaccinations by study arm (Table 49, Table 50, Table 51, Table 52, and Table 53). A comparison of the proportion of subjects reporting solicited symptoms by study arm will be shown in Table 48, and the proportion of subjects reporting solicited symptoms between the first and second study vaccinations will be compared using McNemar's test in Table 54.

Listings of systemic and local solicited events will be presented in Listing 19 and Listing 20, respectively.

Listing 18Listing 19Figure 36Figure 37Unsolicited Adverse Events

Unsolicited, non-serious AEs were documented from the time of the first study vaccination (Day 1 (Visit 01)) through approximately 21 days after the second M-001 study vaccination (approximately Day 43 (Visit 07)), and SAEs were collected through the entire study duration (Day 200). All AEs will be MedDRA coded by for preferred term (PT) and SOC. Serious unsolicited adverse events will be reported by detailed listings showing the event description, MedDRA PT and SOC, relevant dates (study vaccinations and AE), severity, relatedness, and outcome for each event. Non-serious unsolicited AEs will be summarized as number and percentage of subjects reporting at least one event in each MedDRA PT and SOC, cross tabulated by severity and relationship to study product. Additionally, the proportion of subjects and exact 95% CIs (calculated in the same way as above) of AEs in aggregate and by MedDRA categories will be computed.

Unsolicited adverse events by subject will be presented in Listing 21.

The following summaries for unsolicited adverse events will be presented by MedDRA system organ class, preferred term, vaccination and study arm:

- Subject incidence and total frequency of adverse events over time by dose with 95% CI (Days 1-8, Days 9-22) (Table 55);
- Summary of severity and relationship to study product (Table 56);
- Subject incidence and total frequency of related adverse events over time (Table 57);
- Bar chart of AE incidence by severity and MedDRA system organ class and Study Arm (Figure 38);
- Bar chart of total frequency of AEs by relationship to study product and MedDRA system organ class and study arm (Figure 39);

• Bar chart of AE incidence by relationship to study product and MedDRA system organ class and Study Arm (Figure 40).

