11.5.2. Safety Data

Summaries and analysis of safety data will be presented for the Safety Analysis Population.

Solicited AEs will be summarized by severity for each day after each study vaccination (Days 1-8 post each study vaccination) and as the maximum severity over all 8 days. Additionally, solicited AEs will be analyzed by taking the most severe response over the follow-up period, dichotomizing into a binary variable (none versus mild, moderate, or severe) and using standard techniques, such as exact confidence intervals, to summarize the proportion of subjects reporting each symptom, any injection site symptom, and any systemic symptom. Summaries of solicited AEs will be presented separately for each study vaccination as well as overall study vaccinations by treatment arm. The proportion of subjects reporting symptoms may be compared between treatment arms using Chi-square or Fisher's exact test, as appropriate. The proportion of subjects reporting solicited symptoms between the different study vaccinations (e.g., dose 1 vs. dose 2 or dose 3 vs dose 4) will be compared using McNemar's test.

Unsolicited AEs will be coded by Medical Dictionary for Regulatory Activities (MedDRA®) for preferred term and system organ class (SOC). The numbers of SAEs are expected to be small in this trial and will be reported by detailed listings showing the event description, MedDRA® preferred term and SOC, relevant dates (study vaccinations and AEs), severity, relatedness, and outcome for each event. Non-serious unsolicited AEs will be summarized as number and percentage of subjects reporting at least one event in each MedDRA® preferred term and SOC, cross tabulated by severity and relationship to study product. Additionally, the proportion of subjects and exact 95% confidence intervals of AEs in aggregate and by MedDRA® categories will be computed.

Clinical laboratory data will be summarized by severity for each visit and as the maximum over all post-study vaccination visits. Graphical presentations such as box plots will be used to illustrate the change from baseline.

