4.5.1. Safety Variables

Safety will be assessed by the frequency and severity of:

- 1. All SAEs occurring from the time of the first study vaccination through the end of the study
- 2. Solicited AEs reactogenicity events occurring on the day of each study vaccination through 7 days after each M-001 study vaccination:
 - a) Injection site reactions including pruritus, ecchymosis, erythema, induration/swelling, pain, and tenderness.
 - b) Systemic reactions including fever, feverishness, fatigue, malaise, myalgia, arthralgia, headache, and nausea.
- 3. Unsolicited AEs non-serious AEs occurring from the time of the first M-001 study vaccination through approximately 21 days after the second M-001 study vaccination.
- 4. Safety laboratory abnormalities occurring from the time of the first study vaccination through 8 days after the last dose of M-001.
 - a) Clinical safety laboratory parameters measured: WBC, hemoglobin, platelets, ALT, total bilirubin, and creatinine

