14.3.1.1 Solicited Adverse Events

Table 47: Number and Percentage of Subjects Experiencing Solicited Events with 95% Confidence Intervals by Symptom, Dose, and Study Arm*

	Gro	up A:	Dose 1 1 mg M-001 I=X)		Post Doup B:	Placebo		Post Do p A: 1 n (N=X	ng M-001	G	Post Do roup B: 1 (N=X	Placebo		Post Any up A: 1 r (N=X	ng M-001	Gi	Post Any roup B: I (N=X	Placebo
Symptom	n	%	95% CI	n	%	95% CI	n	%	95% CI	n	%	95% CI	n	%	95% CI	n	%	95% CI
Any Symptom	х	xx	x.x, x.x	х	XX	x.x, x.x	х	XX	x.x, x.x	Х	XX	x.x, x.x	х	XX	x.x, x.x	x	XX	x.x, x.x
Any Systemic Symptom																		
Fever																		
Feverishness																		
Fatigue																		
Malaise																		
Myalgia																		
Arthralgia																		
Headache																		
Nausea																		
Any Local Symptom																		
Pain																		
Tenderness																		
Ecchymosis																		
Ecchymosis (measurement)																		
Erythema																		
Erythema (measurement)																		
Induration/Swelling																		
Induration/Swelling (measurement)																		

Table 48: Comparison of the Proportion of Subjects Experiencing Solicited Events by Study Arm

Symptom	Statistic	Group A: 1 mg M-001 Post Either Dose (N=X)	Group B: Placebo Post Either Dose (N=X)
Any Symptom	Proportion	x.xx	X.XX
	95% CI (for proportion)	x.xx, x.xx	x.xx, x.xx
	Difference		X.XX
	95% CI (for difference)		x.xx, x.xx
[Symptom 1]	Proportion		
	95% CI (for proportion)		
	Difference		
	95% CI (for difference)		
[Repeat for all solicit	ed events]	,	1
Note: N=Number of	subjects in Safety Analysis population.		

Table 49: Number and Percentage of Subjects Experiencing Solicited Events by Symptom, Maximum Severity, Dose, and Study Arm*

			Post Do p A: 1 n (N=X	ng M-001		Post Do	Placebo		Post D up A: 1 (N=)	mg M-001	Gı	Post D coup B: (N=	Placebo	P Grou	Post An up A: 1 (N=	y Dose mg M-001 X)	F Gr	Post An Poup B: (N=	y Dose Placebo
Symptom	Severity	n	%	95% CI	n	%	95% CI	n	%	95% CI	n	%	95% CI	n	%	95% CI	n	%	95% CI
Any Symptom	None	х	XX	x.x, x.x	х	XX	x.x, x.x	Х	xx	x.x, x.x	х	xx	x.x, x.x	х	XX	x.x, x.x	Х	xx	x.x, x.x
	Mild																		
	Moderate																		
	Severe																		
Systemic Symptoms	S	1	1	•		•	1			•			1	•		1		•	•
Any Systemic Symptom	None	X	XX	x.x, x.x	Х	xx	x.x, x.x	Х	XX	x.x, x.x	х	XX	x.x, x.x	Х	XX	x.x, x.x	х	XX	x.x, x.x
	Mild																		
	Moderate																		
	Severe																		
Fever	None																		

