Ecchymosis (measurement)	None																				
	Mild																				
	Moderate																				
	Severe																				
	Not Reported																				
Erythema	None																				
	Mild																				
	Moderate																				
	Severe																				
	Not Reported																				
Erythema (measurement)	None																				
	Mild																				
	Moderate																				
	Severe																				
	Not Reported																				
Induration/Swelling	None																				
	Mild																				
	Moderate																				

Table 50: Number and Percentage of Subjects Experiencing Solicited Events by Symptom, Severity, and Day Post Dosing, Group A: 1 mg M-001, Post First Vaccination (Continued)

						Group	A: 1 mg	g M-001	l, Post I	Oose 1 (N=X)										
		Pre-	Dose	Post-	Dose	Da	ıy 1	Da	ıy 2	Da	ıy 3	Da	y 4	Da	ıy 5	Da	ıy 6	Da	ıy 7	Da	ıy 8
Symptom	Severity	n	%	n	%	n	%	n	%	n	%	n	%	n	%	n	%	n	%	n	%
	Severe																				
	Not Reported																				
Induration/Swelling (measurement)	None																				
	Mild																				
	Moderate																				
	Severe																				
	Not Reported																				

Notes: N=Number of subjects in Safety Analysis population who received the specified dose.

Severity is the maximum severity reported post dosing for each subject for each day.

Tables with similar format:

- Table 51: Number and Percentage of Subjects Experiencing Solicited Events by Symptom, Severity, and Day Post Dosing, Group A: 1 mg M-001, Post Second Vaccination
- Table 52: Number and Percentage of Subjects Experiencing Solicited Events by Symptom, Severity, and Day Post Dosing, Group B: Placebo, Post First Vaccination
- Table 53: Number and Percentage of Subjects Experiencing Solicited Events by Symptom, Severity, and Day Post Dosing, Group B: Placebo, Post Second Vaccination

Table 54: Number and Percentage of Subjects Experiencing Solicited Events for Dose 1 Compared with Dose 2 by Study Arm

Study Arm		Dose 2 – Subjects with No Symptoms	Dose 2 – Subjects with Mild or Greater Symptoms	Dose 2 – Total Number of Subjects	McNemar's Test Result (p-value)
Systemic Symptoms	•				
Group A: 1 mg M-001	Dose 1 Subject with No Symptoms	x (%)	x (%)	x (%)	
	Dose 1 Subjects with Mild or Greater Symptoms	x (%)	x (%)	x (%)	
	Dose 1 Total Number of Subjects	x (%)	x (%)	x (100%)	
Group B: Placebo	Subject with No Symptoms				
	Subjects with Mild or Greater Symptoms				

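### Both planned comparisons of solicited reactions contrast none with any; adding a Grade 2-or-higher contrast to Tables 48 and 54 would be a cheap improvement

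*SAP*

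**What the plan says.** SAP 4.5.1 sets the standard: "Safety will be assessed by the frequency and severity of" the listed events, solicited reactions among them. SAP 9.3.1 describes the scale: "They were graded on a scale of 0 (none), 1 (mild), 2 (moderate), and 3 (severe". Each subject is counted once per dose, at the highest grade.

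The scale is then cut. The SAP says "solicited AEs will be analyzed by dichotomizing the response into a binary variable (none vs mild, moderate, or severe"; Protocol 11.5.2 has the same step, "dichotomizing into a binary variable (none versus mild, moderate, or severe".

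Two comparisons are specified in SAP 9.3.1:
- Between arms: "A comparison of the proportion of subjects reporting solicited symptoms by study arm will be shown in Table 48". The shell, titled "Comparison of the Proportion of Subjects Experiencing Solicited Events by Study Arm", gives for each event, after either dose, a proportion per arm and a difference with 95% CI. It has no severity rows and no p-value. Protocol 11.5.2 makes a chi-square or Fisher test of the same proportion optional.
- Between doses, within arm: "the proportion of subjects reporting solicited symptoms between the first and second study vaccinations will be compared using McNemar's test in Table 54". The shell crosses no symptoms with a category headed "Dose 2 – Subjects with Mild or Greater Symptoms", for systemic and for local symptoms.

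Severity is displayed without a contrast in Table 45 (grade by arm), Table 49 (maximum grade by dose and arm, with a CI per grade), Tables 50-53 (by day) and Figures 36-37.

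**The concern.** Reactogenicity of two M-001 doses is a primary safety outcome, and its stated assessment includes severity. At the none/any cut, a mild headache and one that prevents daily activity count the same. Two things are therefore missing.

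- **Between arms.** If M-001 makes reactions worse without adding reactors, the Table 48 difference stays near zero. The excess at Grade 2-3 can be seen in Table 49, but its size and precision as a difference are not given.
- **Between doses.** A subject who goes from mild after Dose 1 to severe after Dose 2 is a concordant pair in Table 54 and adds nothing to McNemar's test. Table 49 gives only the marginal percentages at each dose, so the within-subject change in grade cannot be rebuilt from any summary table.

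The protocol itself treats Grade 2 as a boundary: under Protocol 5.3 an unresolved Grade 2 or 3 event bars a further dose, while Grade 1 is generally permitted. No reason is given for comparing only at none versus any.

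**Working it through.** **Inputs.** From the documents: 60 per arm; grades 0-3; the cut points of Tables 48 and 54. The two-sided 0.05 level is stated only for the immunogenicity t-test and is assumed here. The documents give no reaction rates, so every rate below is an assumption.

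**The plan's own figures for binary safety events.** Protocol Tables 8 and 9 reproduce: 1 - (1 - 0.01)^60 = 45.3%, and the exact 95% CI for 30/60 is 36.8 to 63.2%. Neither bears on where to cut the grade.

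**A worked table.** Let 30/60 in each arm have any symptom, with Grade 2 or higher in 3/60 on placebo and 15/60 on M-001.
- None/any: difference 0.50 - 0.50 = 0. Wald SE = sqrt(2 x 0.25/60) = 0.091, so the 95% CI is -0.18 to 0.18; Fisher p = 1.0.
- Grade 2 or higher: difference 0.25 - 0.05 = 0.20. SE = sqrt(0.25 x 0.75/60 + 0.05 x 0.95/60) = 0.063, so the 95% CI is 0.08 to 0.32; Fisher p = 0.004.

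**Severity-only shift, two arms.** Rejection probability of the chi-square test at 60 per arm, summed over all pairs of binomial counts (Wilcoxon by simulation).
- Any symptom 50% in both arms, Grade 2-3 10% versus 25%: none/any 5%, Wilcoxon on grades 0-3 about 12%, Grade 2 or higher 58%.
- Same any-symptom rates, Grade 2 or higher 5% in controls, exact Fisher test at that cut: 33% power against 15%, 63% against 20%, 85% against 25%, 95% against 30%. None/any by Fisher stays at 3.5%, which is its type I error. Wilcoxon reaches 19% in the 5% versus 25% case.

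**Common odds ratio of 2.5 across grades.** M-001 rate = 2.5 x odds/(1 + 2.5 x odds), where odds = p/(1 - p) on placebo. For example, 50% becomes 2.5/3.5 = 71.4%, and 10% becomes 0.278/1.278 = 21.7%. Chi-square power:

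| Placebo any / Grade 2+ | M-001 any / Grade 2+ | None/any | Grade 2+ |
|---|---|---|---|
| 40% / 10% | 62.5% / 21.7% | 71% | 41% |
| 50% / 10% | 71.4% / 21.7% | 68% | 41% |
| 60% / 15% | 78.9% / 30.6% | 63% | 54% |
| 70% / 20% | 85.4% / 38.5% | 54% | 62% |

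Here none/any is the better cut until the placebo any-symptom rate is high.

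**Dose 1 versus Dose 2.** If 12 subjects in an arm move from mild to moderate or severe and none move back, Table 54 has no discordant pairs. At Grade 2 or higher the discordant pairs are 12 against 0, and exact McNemar p = 2 x 0.5^12 = 0.0005.

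By simulation, assume 57 pairs (60 x 0.95), latent correlation 0.5, Dose 1 grades 35/45/16/4%, an unchanged any-symptom rate, and Grade 2-3 rising from 20% to 38%. McNemar at none/any rejects about 3% of the time, an exact sign test on change in grade about 28%, and McNemar at Grade 2 or higher about 63%. With no change, all three reject about 3% of the time.

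**The case against.** The case for leaving the plan alone has real weight.

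- The primary outcome is worded as occurrence, and none/any is occurrence. That justifies keeping those rows. It does not explain why no contrast uses severity, which SAP 4.5.1 also names.
- Protocol 11.1 tests no safety hypothesis, and Table 48 carries no p-value. This stands: the power figures only illustrate how much each cut can show, and no planned test is underpowered against a stated target.
- Severity is well displayed, and the halting rules act on related Grade 3 reactions. A reader can add moderate and severe in Table 49 and subtract between arms. This stands for the point estimate. The CI of that difference is not printed, and the paired change in grade is not available in any summary table.
- Table 48's cut is inferred from its wording and the dichotomizing sentence before it; Table 54's is explicit. The inference is firm, since the Table 48 shell has no severity rows.

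Stronger readings are tempting. A reader might infer that severity drops out of the report; Tables 45, 49 and 50-53 show otherwise. A reader might infer that none/any is the cut least able to show an excess; the common-odds-ratio table contradicts that at placebo any-symptom rates of about 40-60%. Or a reader might want a rank test on the whole scale as the main remedy; for a severity-only shift it recovers little (about 12% against 58%) because the many subjects with no symptoms are tied.

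**Conclusion.** The gap is real and modest. Solicited reactions are graded, but the two planned comparisons use only whether a reaction occurred. No between-arm difference at Grade 2 or higher is estimated, and within-subject change in grade between doses is not shown.

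The size depends wholly on assumed rates. For a severity-only shift the difference is large: about 5% versus 58% between arms, and about 3% versus 63% between doses. For a shift that also adds reactors, the present cut can be the better one. The two cuts answer different questions, so the second belongs beside the first.

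No stated figure is wrong and no passage is contradicted. This is a cheap improvement to a descriptive analysis, not an error in the plan.

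**What to change.** Keep the any-symptom rows of Table 48 and the existing McNemar test.

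1. **Table 48.** For any systemic symptom, any local symptom and each symptom, add the between-arm difference with 95% CI in the proportion whose maximum functional grade is 2 or higher. A Wilcoxon or proportional-odds comparison is optional.
2. **Table 54.** For systemic and for local symptoms, show the 4x4 table of Dose 1 by Dose 2 maximum grade within each arm, with a McNemar line at Grade 2 or higher. An exact sign test on change in grade is optional. Tabulate subjects who did not receive Dose 2 by their Dose 1 grade: the shell now only counts them in a footnote, and Protocol 5.3 and 5.4.3 make Dose 2 depend in part on earlier reactions.
3. **SAP 9.3.1.** State both cuts and that the added contrasts are descriptive and unadjusted.

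The cost is SAP wording and two table shells, with no new data, visits or subjects. The downside is more unadjusted contrasts: 8 systemic + 6 local + 2 aggregates = 16 in Table 48, and 2 arms x 2 symptom classes = 4 McNemar lines in Table 54. Some will rest on few events, and their wide intervals should be read that way.
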